#### **14.0 RECRUITMENT METHODS**

We have planned for a 36-month enrollment period (see *Timeline*) to recruit 294 couples into the proposed study (~8 couples/month). Our main recruitment strategy will be through the Oregon State Cancer Registry. We have used OSCaR in previous studies allowing us to target recruitments by cancer site and proximity to exercise locations. Between 50%-80% of potential participants in our prior trials are respondents from OSCaR recruiting efforts. Current records indicate that there are 2616 living persons who were diagnosed with PC, BC and CRC in Oregon, that are between the ages of 40-70 years old, within 2 years of diagnosis, and who live within a 10-mile radius of the Portland metro area. Based on our prior recruitment for our pilot of *Exercising Together* and GET FIT using OSCaR, 28% respond to recruitment letters and of those 65% were eligible and then 55% enroll, for an overall enrollment rate from the registry of 10%. Using OSCaR for the current trial would be expected to yield **261 participants**, close to our target sample size. Other strategies that we will employ are: 1) Clinician referral through OHSU Hospital and Community Oncology clinics that serve outer Portland area. Physicians referral accounted for ~15% of past enrollees and, 2) Direct community recruitment using newspaper ads, radio, web and presentations at cancer organizations and conferences, which recruited 25% of participants in our previous cancer exercise trials. Patients may also be recruited through Tuality Healthcare, or Adventist Medical Center. Additional recruitment will occur by obtaining data (name, phone number, email, address, cancer diagnosis and treatment information) from OCTRI's Cohort Discovery, OCTRI's Research Data Warehouse, and OHSU's Medical Records. After obtaining this demographic data, recruitment will occur via letters, e-mails, phone calls, or letters/announcements via MyChart.

This study will use Epic MyChart® to recruit potential participants. Researchers will work with ITG and/or OCTRI to identify potential participants based upon the above eligibility criteria. Researchers will create a Reporting Workbench query in epic based on inclusion and exclusion criteria. Potential participants will be sent a MyChart® recruitment message asking them to participate. There is no risk of duplicate invitations as it is based on MyChart® accounts combined with Epic records and no duplication is possible.

Clinical practice head at each site will be contacted about the study and their permission will be obtained before any message is sent.

Ancillary study: Participants may also be recruited through the Oregon Office of Rural Health or the Oregon Rural Practice-based Research Network.

## **15.0        INFORMED CONSENT (REQUIRED, UNLESS A WAIVER OR ALTERATION IS APPROVED BY THE IRB)**

Written informed consent will be obtained from all participants. A copy of the consent form and documentation of consent will be maintained in the participant's medical record as well as stored in a study file kept in a locked cabinet in the Knight Cancer Research Building (for paper documents only) or stored on an encrypted and password protected computer drive in the OHSU Knight Cancer Research Building (for electronic consents and scanned PDFs of paper consents). Electronic data, including the electronic consent, will also be stored in a web-accessible REDCap database housed on an OHSU secure server.

Interested and eligible participants will go to OHSU Knight Cancer Research Building to meet with the study coordinator to sign an online IRB-approved Consent Form prior to any study-related procedure. The Consent Form will describe the goals of the study, study procedures, confidentiality, risks, benefits, and voluntary nature of the research. After they view the consent online, and click the box that they have read and agree to participate (indicating that they have signed the consent), they will be sent links and requested to complete REDCap surveys. The study coordinator and PI will make themselves available throughout the consent process to answer any questions regarding the study. The study coordinator will ask the participant to reflect back the details of the study to ensure the participant's understanding. The participant will also be given a copy of the consent form to take home and refer to whenever needed. Participants will be told that participation is voluntary and they may discontinue participation at any time and that participation will not affect their usual care at OHSU.

During periods of hospital recommendations for decreased in-person contact, re-consent for the modified procedures will be done over the phone or via teleconference. Study team members will inform the participants of the modified procedures and note their verbal agreement to continue on the study.

Individuals who have not previously consented will consent by an electronic consent process setup through OCTRI's REDCap system (See 17.0 for a description of REDCap's Privacy, Confidentiality, and Data Security). A waiver of documentation of consent will be used to waive the need for a legally valid signature, however, an electronic signature and affirmation of consent will be collected in REDCap. Study staff will sign an attestation form in REDCap after the participant consents. Study staff will proceed with following the outline for remote testing procedures, as previously described in section 3.0 Study Design/Methodology.

Ancillary study: Individuals being recruited for the ancillary study will consent by an electronic consent process setup through OCTRI's REDCap system (See 17.0 for a description of REDCap's Privacy, Confidentiality, and Data Security). A waiver of documentation of consent will be used to waive the need for a legally valid signature, however, an electronic signature and affirmation of consent will be collected in REDCap. Study staff will sign an attestation form in REDCap after the participant consents. Study staff will proceed with following the outline for remote testing procedures, as previously described in section 3.0 Study Design/Methodology.

## **16.0 CHANGES TO PROTOCOL**

Any modification of this protocol must be documented in the form of a protocol revision or amendment signed by the principal investigator and approved by the Knight Cancer Institute and the IRB before the revision or amendment may be implemented. The only circumstance in which the amendment may be initiated without regulatory approval is for a change necessary to eliminate an apparent and immediate hazard to the patient. In that event, the investigator must notify the IRB in writing within 5 working days after the implementation.

## **17.0 PRIVACY, CONFIDENTIALITY, AND DATA SECURITY**

Standard institutional practices will be followed as described in the OHSU Information Security and Research Data Resource Guide ([http://ozone.ohsu.edu/cc/sec/isg/res\\_sec.pdf](http://ozone.ohsu.edu/cc/sec/isg/res_sec.pdf)) to maintain the confidentiality and security of data collected in this study. Study staff will be trained with regard to these procedures.

Paper files will be stored in locked filing cabinets in restricted access offices at OHSU Knight Cancer Research Building.

Electronic data will be stored on an encrypted and password protected computer drive in the OHSU Knight Cancer Research Building.

Electronic data will also be stored in a web-accessible REDCap database housed on an OHSU secure server. Features of REDCap that protect participants' privacy and data security include:

- Physical Security: OCTRI's REDCap software is housed on servers located in ITG's Advanced Computing Center providing locked physical security
- Electronic Security: The REDCap servers are housed behind both the OHSU firewall and a second ACC firewall. All web-based data transmissions are encrypted with industry-standard SSL methods.
- Controlled User Access: REDCap is employs a robust multi-level security system that enables researchers to easily implement "minimum necessary" data access for their research staff, including specification of data fields that are identifiers. This feature includes "single click" ability to provide completely deidentified (removing all identified data fields and shifting dates) for analysis or other purposes. User activities are logged to enable auditing of all data access. Access is integrated with OHSU's network such that users who are also OHSU employees are authenticated against their OHSU network credentials.
- Data Integrity: REDCap is jointly managed in accordance with OHSU Information Security Directives by ACC staff and members of OCTRI's Biomedical Informatics Program, ensuring fidelity of database configuration and back-ups. User activities are logged to enable auditing of all data changes.

Access to data/specimens is restricted to study personnel and requires OHSU ID/password authentication.

Upon enrollment, subjects will be assigned a code that will be used instead of their name, medical record number or other personally identifying information. Electronic files for data analysis will contain only the subject code.

Codes will not contain any part of the 18 HIPAA identifiers (initials, DOB, MRN)

The key associating the codes and the subjects personally identifying information will be restricted to the PI and study staff. The key will be kept secure on a restricted OHSU network drive in a limited access folder.

Data will be transferred in files using encryption.

Data/specimens released to other investigators will be labeled with only the code.

Data/specimens from this study will be banked in a repository for future use as part of this protocol. Access to data/specimens is restricted to study personnel.

## **18.0 OHSU IRB REPORTING OF UNANTICIPATED PROBLEMS AND ADVERSE EVENTS**

Reportable New Information (RNI) will be reported to IRB according to the policies, procedures and guidelines posted on the [OHSU IRB web site](#):

- Fatal and life-threatening events will be reported to OHSU IRB within 5 days of notification of the event. All other reportable events will be submitted to OHSU IRB no later than 5 working days of occurrence or notification of the event. Copies of the report documents will be kept in the study regulatory binder.
- Reportable events are submitted through OHSU eIRB and will be reviewed by OHSU Knight Cancer Institute DSMC and IRB.

## **19.0 OHSU KNIGHT CANCER INSTITUTE DATA AND SAFETY MONITORING PLAN**

In addition to complete study and pharmacy files, complete records must be maintained on each patient enrolled on this protocol. OHSU Knight Clinical Research Quality and Administration (CRQA) shared resource is responsible for ensuring that all member investigators and affiliate investigators conduct clinical research studies in compliance with local IRB standards, state laws, FDA regulations (where applicable), Department of Health & Human Services (DHHS) regulations and NIH policies. The Data and Safety Monitoring Committee (DSMC) is responsible for conducting Quality Assurance audits on Knight approved protocols according to the Data and Safety Monitoring Plan, policies and procedures. Locally initiated observational and low risk interventional studies may be audited by an OHSU Knight DSMC audit team any time after enrollment begins. The Quality Assurance audit process provides assurance that the reported data accurately reflects the data in the primary patient record and that regulatory requirements are met.

### **19.1 Monitoring Plan:**

This study represents a moderate risk to study participants because it is a clinical trial involving human subjects. Though physical activity and exercise may be associated with adverse events (e.g. tiredness, muscle soreness, muscular injury, cardiac events, shortness of breath), most such events are associated with inappropriately vigorous exercise, which is not the objective of this study. The study will be wholly overseen by the OHSU NCI-designated Cancer Institute for both safety and compliance to institutional and NCI policies. The PI is responsible for evaluating each adverse event as it occurs and for notifying the OHSU IRB of the occurrence of an adverse event according to IRB protocols. An interim safety/efficacy review will occur early in the intervention

period to determine potential safety concerns or benefits of the intervention well before the total sample has been accrued. The interim safety review will be overseen by OHSU Knight Data Safety and Monitoring Committee (DSMC, see details below) and will occur after the first 50 enrolled couples (~25% of total sample) have completed 3 months of exercise training to assess early for program safety. The efficacy review will be conducted by an independent monitor, [name], a biostatistician and measurement expert in the OHSU Knight Cancer Institute and Oregon Clinical Translational Research Institute (OHSU's CTSA) and not a member of the study personnel, after the first 50 couples (100 participants) have completed their first post-intervention (6 month) testing appointment.

Adverse events related or possibly related to exercise sessions (i.e., group exercise classes, prescribed home program exercise, and physical performance measurement appointments) will be graded according to their significance for severe consequences, such as injury or death, using the following grades determined by the OHSU IRB.

Examples of serious adverse events (life-threatening or disabling and requiring medical attention). Serious adverse events that may occur during exercise in this study include death and cardiovascular events, though these are extremely rare in the absence of significant cardiac pathology.

Examples of moderate adverse events (resolve with treatment). Moderate adverse events that may occur during exercise include symptoms, such as shortness of breath and orthostatic intolerance.

Examples of mild adverse events (do not require treatment). Reports of side effects, such as muscle soreness, moderate tiredness while exercising, and similar discomforts are mild adverse events.

Examples of unexpected adverse events that do not include physical harm. Adverse events can also include breaches of confidentiality, emotional harms, or complaints about study procedures or conduct of investigators.

In this study we do not anticipate moderate or serious adverse events. Only moderate and serious adverse events that are related or possibly related to exercise sessions (i.e., group exercise classes, prescribed home program exercise, and physical performance measurement appointments) will be reported on our Adverse Events Log.

A survey (Adverse Events Survey) was created by the study team to be administered monthly during the participants' year long participation in the study. Adverse events reported through this survey may be followed-up by study staff with a phone call, e-mail, or in person in class during the intervention period, when participants self-report that their reporting condition is due to a study-related exercise activity or if more information is needed to determine reportability. Participants will also have the opportunity to report adverse events during exercise class, the home-program phone calls, or at physical performance measurement appointments.

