#### **Study Arms**

All Programs: Regardless of group assignment, all participants will be expected to engage in 1-hr exercise sessions, 2 d/wk for 6 months. For participants assigned to supervised exercise training, both arms will be held at the same location within a wave and in a similar block of time to aid in enrollment, but scheduled in a way to reduce contamination (i.e., there will be 15 minutes between the end of *Exercising Together* and the beginning of Survivor-Spouse/Partner Group classes. The latter are run at the same time, but in different rooms at a single location). Class size will be limited to 9-10 couples per class (Arm 1) or 9-10 persons in a spouse/partner or survivor class (Arm 2) so that enough attention is given to participants to ensure proper form and safety. For participants assigned to home-based training they can opt to exercise at a facility or to follow an instructional DVD at home (see below).

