**Survivor / Spouse/Partner Home Training:** Participants will be given equipment (vest, weights and/or resistance bands) and a program to do at home or a facility, depending on their preference. Within two weeks of randomization, each couple will have two one-hour training sessions with an exercise trainer who will teach them our functional strength training program, modified to their abilities and for home or facility use. We will also provide them with a general DVD of the strength program to follow at home. The trainer will check in weekly by phone in month 1 and monthly thereafter to assess tolerance and modify programs as needed. We have delivered home-based resistance training this way in our prior studies without any related injuries [42-44]. Participants can perform the program on days (allowing for 48 hours between sessions) and at times convenient for them. There is no requirement that partners exercise at the same time, though we will track the degree to which couples may do so in case we need to account for this in analyses.

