#### **Intervention, tests or procedures:**

Regardless of group assignment, all participants will be expected to engage in 1-hr exercise sessions, 2 d/wk for 6 months. The basic training program for all three study arms is a functional strength training program based on recommendations for improving muscle strength in adults[41] and our prior studies in cancer survivors. For safety reporting purposes, a monthly Adverse Event Survey will be sent electronically or completed over the phone. More details about this survey can be found under section 19.1 Monitoring Plan.

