## **19.2. Plan for Reporting Adverse Events**

Serious adverse events will be reported immediately to the Principal Investigator (PI), who will immediately notify all other investigators. The PI will file a full written report to the OHSU Institutional Review Board (IRB) within 24 hours of notification of the serious event, as required by the OHSU IRB. Specifically, the following will be reported, in writing: 1) all deaths in study

participants, during the intervention period, regardless of cause, 2) all serious adverse events associated with the study procedures

Moderate adverse events will be tabulated by the PI, who will notify members of the research team if trends are identified. If trends are noted, preventive measures will be implemented, such as providing education of participants in the study to emphasize prevention of the adverse event. Moderate adverse events will be included in annual reports to the OHSU IRB.

Mild adverse events will not be formally logged but, participants will receive advice on avoiding such events.

Unexpected adverse events that do not include physical harm, usually having to do with study procedures, will be reported within 10 days to OHSU IRB, using a written report form.

Adverse events will be reported to NIH according to NIH protocols.

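### The Adverse Events Log keeps only exercise-related events, and class arms have more staff contacts than the home arm, so arm differences in logged non-fatal events may be confounded by ascertainment

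*Combined protocol and SAP*

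**What the plan says.** **What reaches the log.** Section 19.1 admits to the log "Only moderate and serious adverse events that are related or possibly related to exercise sessions", and it provides for grading only of events with that link. Section 19.2 adds: "Mild adverse events will not be formally logged". Deaths fall outside the relatedness filter: Sections 19.2 and 19.3 require them to be reported whatever the cause.

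**The channel common to all arms.** Section 8.0 says that "a monthly Adverse Event Survey will be sent electronically or completed over the phone". The Schedule of Events runs it from month 1 to month 12. Under Section 19.1, staff may follow up a survey report "when participants self-report that their reporting condition is due to a study-related exercise activity or if more information is needed to determine reportability". Follow-up is permitted, not required, and one listed route is in person in class.

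**The channels that differ by arm.** Section 19.1 continues: "Participants will also have the opportunity to report adverse events during exercise class, the home-program phone calls, or at physical performance measurement appointments". Section 3.0 (Study Arms) sets the session schedule: "Regardless of group assignment, all participants will be expected to engage in 1-hr exercise sessions, 2 d/wk for 6 months". An instructor leads these sessions in the two class arms. In the home arm each couple has two training sessions with a trainer, and then: "The trainer will check in weekly by phone in month 1 and monthly thereafter to assess tolerance and modify programs as needed".

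**Who judges.** The principal investigator evaluates each event (Section 19.1). The only blinding described is that of the research assistants who do the testing (Section 8.0). No assessment of relatedness blind to arm is described.

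**The concern.** Whether a non-fatal event appears in the log depends on two things that can differ by arm apart from the event itself. One is whether a staff member hears of it. The other is whether someone who knows the arm links it to exercise. An instructor who sees a strain happen in class can attribute it at once. The same strain in an unsupervised session at home may surface weeks later, on a call or in a survey, with a weaker link to exercise. A moderate or serious event judged unrelated has no planned grade and no log entry in any arm.

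The log informs decisions. Section 19.1 plans a safety review by the data and safety monitoring committee after the first 50 couples have completed 3 months of training. Section 19.2 has the principal investigator look for trends in moderate events and act on them. A trial of supervised against unsupervised exercise will also be read for safety by arm. If the log finds events more readily in classes, supervised exercise could look less safe than it is, or home exercise safer.

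**Working it through.** The documents give no contact count, contact ratio or expected event rate, so there is no stated figure to reproduce. The counts below follow from the schedules.

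**Contacts specific to an arm, 6 training months**
- Class arms: 2 sessions per week × 24 to 26 weeks = 48 to 52.
- Home arm: 2 training sessions + 4 weekly calls in month 1 + 5 monthly calls in months 2 to 6 = 11. The plan gives no end date for the monthly calls; I assume they stop when training stops.
- Ratio: 52 / 11 = 4.7.
- Range: 48 / 12 = 4.0 (month 1 taken as five weeks) to 52 / 9 = 5.8 (calls only).

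**Adding the channels shared by all arms**
- Over 6 months, 6 surveys and 2 testing visits: (52 + 8) / (11 + 8) = 60 / 19 = 3.2.
- Over 12 months, 12 surveys and 3 testing visits: (52 + 15) / (11 + 15) = 67 / 26 = 2.6.

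**Allowing for attendance.** Section 13.0 sets the completer threshold at 50% of sessions. At that level the class count is 26, and the 6-month ratios become 26 / 11 = 2.4 (arm-specific) and (26 + 8) / (11 + 8) = 34 / 19 = 1.8 (all channels).

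**From contacts to bias.** A contact count is not a probability of detection. As an illustration, let true rates be equal in all arms, let the survey find a share *s* of events, and let arm-specific contacts independently find a share *c*. Then P(found) = 1 − (1 − *s*)(1 − *c*), and the spurious class-to-home ratio is the quotient of the two values. All values of *s* and *c* below are assumptions; none comes from the documents.

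| Class *c* | Home *c* | *s* = 0 | *s* = 0.5 | *s* = 0.8 |
|---|---|---|---|---|
| 0.9 | 0.5 | 0.90 / 0.50 = 1.80 | 0.95 / 0.75 = 1.27 | 0.98 / 0.90 = 1.09 |
| 0.9 | 0.3 | 0.90 / 0.30 = 3.00 | 0.95 / 0.65 = 1.46 | 0.98 / 0.86 = 1.14 |

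The spurious ratio runs from 1.09 to 3.0, and what moves it most is how well the common survey works. The model covers detection only. Filtering on relatedness comes afterwards and could widen or narrow the gap.

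**The case against.** The strongest reply is that the monthly survey reaches everyone for 12 months, testing visits occur in all arms, possibly related events are kept, and unclear cases can be pursued. All of this is correct, and it is why the ratio with shared channels is the fairer one. It does not remove the problem, because discretionary follow-up and the relatedness filter are applied after the survey, and follow-up in class is open only to the class arms.

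Several further points stand:
- Section 13.0 specifies no comparison of adverse events between the randomized arms. It compares event counts only between the ancillary study and the parent trial. The issue is therefore how safety data are recorded and read, not a fault in a planned test.
- A trainer call made to assess tolerance may reveal more than one session in a class of 9 to 10 couples or persons. Supervised sessions may also be held by videoconference, so an instructor is not always in the room.
- Section 9.0 stores answers to study surveys in REDCap. If that covers the Adverse Events Survey, part of the unfiltered information will exist even though the log omits it.

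A reader might infer that follow-up rests mainly on the participant's own attribution. The text gives two triggers joined by *or* and ranks neither. A reader might also infer that serious events at home will simply be missed. Deaths are reported whatever the cause, and other events can surface by survey, call or testing visit.

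**Conclusion.** The concern holds in a limited form. The logging rule passes non-fatal events through attribution that is not blinded and through staff contact that differs by arm. Arm differences in logged events may therefore be confounded, probably towards more logged events in the class arms. The contact imbalance is about 4.7 to 1 on arm-specific contacts at full attendance, 3.2 to 1 over 6 months with shared channels, and 2.6 to 1 over 12 months.

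It would be tempting to say that any arm difference in the log simply reflects ascertainment, or that the contact ratio measures the bias. The documents support neither. Supervision may change true event rates as well as detection, and the sensitivity of the survey is not given. The bias could be small or substantial. Deaths are unaffected, and the efficacy analyses do not depend on the log.

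**What to change.** In Section 19.1, enter on the log every moderate or serious event reported in the monthly survey, in all three arms, whether or not it is thought to be related to exercise. Record source (survey, class, call, testing visit) and relatedness as separate fields. Extend grading to these events, since it now covers only exercise-related ones.

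For the interim safety review and the final safety report, tabulate survey-reported events by arm regardless of attribution, and show class-, call- and visit-reported events separately. Relatedness can still be shown, as a column and not as a condition of entry.

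Reconcile Section 10.0 (Protection Against Risk), which has minor as well as major complaints documented and tracked to evaluate safety, with Section 19.2, which leaves mild events off the formal log.

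The cost is two extra fields, more log entries and slightly more staff time; the survey already goes to everyone each month. The change removes the relatedness filter and the dependence on staff contact from the main safety table. It does not remove differences in how participants who know their arm answer the survey.
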